# A PROSPECTIVE NON-RANDOMIZED UNBLINDED STUDY EVALUATING THE TREATMENT OF KNEE OSTEOARTHRITIS WITH THE CRYOTOUCH III DEVICE

# **MYO-0601 REV 04**

**Author: [name] Revision History:** 

Revision	Description	Justification	DCO#	Release Date
01	Initial Release.	Initial Release	N/A	10/15/2012
02	Updated the Schedule of Events in Appendix B	Schedule of Events for Visit 5 did not originally reflect the requirement for completion of Subject Post-Treatment Questionnaire as required by protocol	N/A	11/27/2012
03	Increase enrollment Enrollment based on number of subjects rather than number of "treatments Remove "lidocaine with epinephrine" and replace with "Local anesthesia"  Spelling and grammar edits	Allow for additional enrollment Provide clarification  Allow investigators to use local anesthetic of choice to achieve complete cutaneous anesthesia Provide clarification	N/A	12/19/2012
04	Define end of study  Remove secondary endpoint: Analgesic Use	Provide end date of Day 84 for any subject who has treatment effect at or beyond Day 56 Data not collected for this secondary endpoint	1740	6/25/2013

# **Protocol Synopsis**

Title	A Prospective Non-Randomized Unblinded Study Evaluating the Treatment of Knee Osteoarthritis with the Cryo-Touch III Device		
Study Device	Cryo-Touch III (a.k.a. PCP 1.0)		
Study Objective	A proof of concept study to evaluate the feasibility of safe and effective treatment through optimization of the Cryo-Touch III device for temporary relief of pain.		
Treatment Groups	Multiple		
Duration of Study	Enrollment and follow-up is expected to take approximately 4 months. A subject will participate for approximately 10 weeks.		
Study Population	Healthy subjects, male or female, ages 18 and older with chronic knee pain related to a diagnosis of osteoarthritis of the knee.		
Total Number of Subjects	Up to 50 subjects will be enrolled.		
Number of Sites	1-2		
Inclusion Criteria	
 
Eligible subjects must meet the following criteria:
 
Male or female, 18 years of age and older.
 
Trial participants must meet American College of Rheumatology (ACR) criteria for osteoarthritis of the knee (unilateral or bilateral).
 
Any medications must be maintained on a stable schedule for at least two weeks prior to treatment. No washout period is allowed.
 
Must have an average score for pain of ≥ 4 Visual Analog Scale (VAS) over the last 30 days.
 
Subject is willing and able to give written informed consent.
 
Subject is willing and able to comply with study instructions and commit to all follow-up visits for the duration of the study.
 
Subject is in good general health and free of any systemic disease state or physical condition that might impair evaluation or which in the investigator's opinion, exposes the subject to an unacceptable risk by study participation.
 
		
Exclusion Criteria	
 
A subject is ineligible if one or more of the following criteria applies:
 
A partial or full knee replacement (in the treated knee).
 
Any use of systemic injections (in any area) within the last 6 months.
 
Current enrollment in an investigational drug or a device study that specifically targets pain treatment.
 
Any additional diagnosis that in the opinion of the investigator directly contributes to knee pain.
 
		

	
 
Any concomitant inflammatory disease or other condition that affects the joints (e.g. rheumatoid arthritis, metabolic bones disease, gout, active infection, etc.)
 
Any clotting disorder and/or has used an anticoagulant (e.g., warfarin, clopidogrel, etc.) within seven (7) days prior to administration of the device.
 
Allergy or intolerance to local anesthetic.
 
Any local skin condition at the treatment site that in the investigator's opinion would adversely affect treatment or outcomes.
 
Any chronic medical condition that in the investigator's opinion would prevent adequate participation.
 
Any chronic medication use (prescription, over-the-counter, etc.) that in the investigator's opinion would affect study participation or subject safety.
 
For any reason, in the opinion of the investigator, the subject may
 
			
	not be a suitable candidate for study participation (i.e., history of noncompliance, drug dependency, any related knee injury due to a worker's compensation claim, etc.).			
Study Visit Schedule	
 
Visit 1/Screening (-30 Days to Day 0)
 
Visit 2/Treatment (Day 0)
 
Visit 3/ Maintenance (Day 7)
 
Visit 4/ Maintenance (Day 30)
 
Visit 5/Study Exit (Day 56) – Telephone Follow-Up
 
			
Primary Outcome	An improvement in the Visual Analog Scale (VAS) for pain at Day 7.			
Secondary Outcomes	
 
Improvement (pain, stiffness, and functionality) as determined by the Western Ontario and McMaster Osteoarthritis Index (WOMAC) Scale at Day 7. A significant difference is observed as ≥ 2-points.
 
Duration of Treatment Effect
 
			

### 1. Introduction

# 1.1. Background

Over 100 million patients in the United States suffer from chronic pain. Chronic pain conditions are often debilitating, taking a toll on a patient's physical and mental welfare. Though a variety of pain management techniques currently exist, the most common nonsurgical options provide slow-acting and/or short-term relief. Medication, often in the form of non-steroidal anti-inflammatory drugs (NSAIDs) and opioids, comes with an array of side effects such as nausea and vomiting. Medication also presents the possibility of more serious effects such as increased risk of heart attack and stroke, and tolerance or dependency issues. Surgical strategies tend to be reserved for more severe cases and are limited by the risks and complications typically associated with surgery including bleeding, bruising, scarring, and infection. A nonsurgical, minimally invasive, long-lasting approach to chronic pain management is desirable.

Myoscience, Inc. (Redwood City, CA) has developed a pain management device – the Cryo-Touch III – for a novel, minimally invasive procedure using focused cold therapy to target sensory nerve tissue and offer long-lasting pain relief through cryoanalgesia. The device operates on the well-established cryobiology principle that localized exposure to controlled moderately low temperature conditions can alter tissue function. The therapy treats nerves with low temperatures via a cold probe in the form of an assembly of small diameter needles, creating a highly localized treatment zone around the probe. This focused cold therapy creates a conduction block that prevents nerve signaling. Prior studies of Cryo-Touch, Cryo-Touch II, Cryo-Touch III (a.k.a. PCP 1.0) have provided preliminary evidence of effectiveness on motor nerves and have been shown to be safe with no serious device-related adverse events.

[figure not shown]
Though studies have proven efficacious in targeting motor nerves, the device's effect on sensory nerves has yet to have been investigated in the clinical setting. The goal of the study described herein is to evaluate the degree and duration of effect of the Cryo-Touch III in reducing chronic pain by targeting sensory nerves.

# 1.2. Device Description

The Cryo-Touch III device (a.k.a. PCP 1.0) (Figure 1) is a minimally invasive needle-based device. The device consists of a re-usable portable Control Unit, Handpiece, single use Cryoprobes (Figure 2) and Cryogen Cartridges. The Control Unit and Handpiece are powered by the Control Unit utilizing connection to a standard power outlet and is microprocessor controlled. Its functionality is driven by an operator controlled on/off switch. The unit displays indicator lights to guide the operator. The system produces the desired effects through initiation

of a cooling cycle. Each cooling cycle is initiated by subcutaneous insertion of the Cryoprobe into the selected site and activation of the cryogen flow. A freezing zone forms around the tip of the Cryoprobe and the adjacent tissue. The Cryogen Cartridges are provided in individually sealed pouches. Each cartridge contains a nitrous oxide cylinder encased with a safety cap and filtering. The Cryoprobes are supplied in sterile packaging and are single-patient use. The Cyroprobe tips are closed, no cryogen enters the insertion site. A skin warmer provides warming at the base of the Cryoprobe tips to keep the surface above freezing temperatures.

- A. Control Unit
- B. Handpiece
- C. Cryoprobe
- D. Cryogen Cartridge

Figure 1. Picture of Cryo-Touch III device.

[figure not shown]

Figure 2. Picture of the Cryoprobe.

- A. Skin Warmer
- B. Cryoprobe Tips

### 1.3. Regulatory Status

The myoscience Cryo-Touch III device has been cleared by the U.S. FDA as a class II medical device, K120415. Approved indications include general tissue destruction during surgical procedures and cryo-treatment of nerves to block pain.

Additionally, myoscience and an independent review board has determined that the Cryo-Touch III device is a non-significant risk device under 21 CFR §812.2(b) as described for use within this protocol.

Therefore, an approved Investigational Device Exemption (IDE) from FDA is not required to legally perform the study described herein in the US.

# 2. Study Protocol

# 2.1. Design

This is a prospective non-randomized unblinded study.

# 2.2. Study Duration

Enrollment and follow-up is expected to take approximately 4 months.

# 2.3. Sample Size

Up to 50 subjects will be enrolled.

# 2.4. Subject Inclusionary Criteria

- 1. Male or female, 18 years of age and older.
- 2. Participants must meet American College of Rheumatology (ACR) criteria for osteoarthritis of the knee (unilateral or bilateral). Clinical criteria includes knee pain and at least three of the following 6 criteria: 50 years of age or older, stiffness lasting less than 30 minutes, crepitus, bony tenderness, bony enlargement, and/or no warmth to the touch.
- 3. Any medications (prescription and/or over-the counter) must be maintained on a stable schedule for  $\geq 2$  weeks prior to treatment. No washout period is allowed.
- 4. An average Visual Analog Scale (VAS) for pain  $\geq$  4 over the last 30 days.
- 5. Subject is willing and able to give written informed consent.
- 6. Subject is willing and able to comply with study instructions and commit to all follow-up visits for the duration of the study.

7. Subject is in good general health and free of any systemic disease state or physical condition that might impair evaluation or which in the investigator's opinion, exposes the subject to an unacceptable risk by study participation.

### 2.5. Subject Exlusionary Criteria

- 1. A partial or full knee replacement (in the treated knee).
- 2. Any use of systemic injections (in any area) within the last 6 months.
- 3. Current enrollment in an investigational drug or a device study that specifically targets pain treatment.
- 4. Any additional diagnosis that in the opinion of the investigator may directly contribute to knee pain.
- 5. Any concomitant inflammatory disease or other condition that affects the joints (e.g. rheumatoid arthritis, metabolic bones disease, gout, active infection, etc.).
- 6. Any clotting disorder and/or has used an anticoagulant (e.g., warfarin, clopidogrel, etc.) within seven (7) days prior to administration of the device.
- 7. Allergy or intolerance to local anesthetic.
- 8. Any local skin condition at the treatment site that in the investigator's opinion would adversely affect treatment or outcomes.
- 9. Any chronic medical condition that in the investigator's opinion would prevent adequate participation.
- 10. Any chronic medication use (prescription, over-the-counter, etc.) that in the investigator's opinion would affect study participation or subject safety.
- 11. For any reason, in the opinion of the investigator, the subject may not be a suitable candidate for study participation (i.e., history of noncompliance, drug dependency, any related knee injury due to a worker's compensation claim, etc.).

# 2.6. Schedule of Events

See Appendix B.

### **2.6.1.** Visit 1/Screening (Day -30 to Day 0)

Subjects will be informed of all study activities and requirements. After the subject has had ample opportunity to ask and have questions answered an informed consent form will be signed and a copy provided to the subject.

The investigator, or designee, will document the subject's medical history, demographic information, concomitant medications/concurrent procedures, and any other required data points to determine subject eligibility.

Once the subject is determined to be eligible, the subject will be scheduled for the next visit. The Screening Visit 1 and Treatment Visit 2 may occur on the same day. Every effort will be made to reduce the time between Screening and Treatment Visits if possible.

### 2.6.2. Visit 2/Treatment (Day 0)

### 2.6.2.1. Pre-Treatment/Evaluation Preparation

No special preparation by the subject is required prior to the treatment. The investigator will reaffirm eligibility criteria and the subject's willingness to continue participation in the trial. Any changes in concomitant medications/concurrent procedures will be recorded. Any adverse events that may have occurred prior to treatment will be documented as a change in medical history.

Non-invasive ultrasound imaging of the treatment area may be captured. Nerve stimulation may be used to assess location of nerves via a percutaneous nerve stimulator or a transcutaneous nerve stimulator.

The Cryo-Touch III device will be used on awake subjects who are prepared with dermal anesthesia only. The skin in the treatment area will be cleansed with alcohol. Local anesthetic will be injected into target sites with the goal of complete cutaneous anesthesia at the target treatment areas prior to the treatment.

The target of treatment is the infrapatellar branch of the saphenous nerve. The nerve will be accessed by locating adjacent landmarks and treating in a linear fashion to capture the nerve as it travels inferiorly (see Figure 3).

Subjects with a bilateral indication will receive treatment in both knees.

[figure not shown]

Figure 3: Nerve map of intended treatment.

### **2.6.2.2.** Treatment

The Cryo-Touch III device will have been prepared by the trained investigator (or Sponsor designee) according to the *Instructions for Use (IFU)* as provided by myoscience (see supplementary material). Representatives of myoscience may be present at the treatment. Photography of the treatment area may be taken. Videography may also be captured during the treatment.

Varying treatment algorithms will be pre-determined by the sponsor and placed into cohorts as appropriate for anyalysis. This is intended to determine the most effective method of treatment and device optimization. Algorithms may include the following parameters: temperature, length of treatment, number of treatment cycles, probe tip design, and probe length.

If at any time the device does not perform as expected the investigator (or designee) we follow procedures as outlined in the IFU.

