### 3.1.1. Primary Outcome Measure

Improvement of knee pain as measured on the Visual Analog Scale (VAS) for pain at Day 7 as compared to baseline (Day 0). See Appendix.

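### Does Section 2.6.2.2 promise more than non-randomised cohorts within 50 subjects can show, and does the plan need to change for it?

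*Protocol*

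**What the plan says.** Section 2.6.2.2 of the Protocol states: "Varying treatment algorithms will be pre-determined by the sponsor and placed into cohorts as appropriate for anyalysis". It gives the purpose in the next sentence: "This is intended to determine the most effective method of treatment and device optimization". It then lists what may vary: "Algorithms may include the following parameters: temperature, length of treatment, number of treatment cycles, probe tip design, and probe length". That is five parameters. The number of cohorts, their sizes and the way subjects reach them are not given; the synopsis lists the treatment groups only as multiple.

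Other sections set the frame. Section 2.1: "This is a prospective non-randomized unblinded study". Section 2.3: "Up to 50 subjects will be enrolled". The synopsis gives the objective as "A proof of concept study to evaluate the feasibility of safe and effective treatment through optimization of the Cryo-Touch III device". Section 3.1.1 defines the primary outcome as improvement in VAS knee pain at Day 7 compared with Day 0, a change within each subject. Section 1.1 puts the goal as evaluating how large the pain reduction is and how long it lasts.

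**The concern.** To determine which method is most effective is to make a comparison, and this design supports comparisons weakly. Subjects are not randomised to algorithms, nobody is blinded, and the outcome is pain that the subject reports. A cohort could look better for reasons unrelated to its algorithm:

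- **Selection.** Section 2.5, item 11, lets the investigator exclude a subject judged unsuitable.
- **Time and learning.** Section 1.1 says the device's "effect on sensory nerves has yet to have been investigated in the clinical setting", so operators may improve as they gain experience with this target.
- **Expectation.** Subjects and staff know what is being given.

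More subjects would not remove such bias; they would only make a false ranking more stable. Small cohorts add chance error. The wording on placing algorithms into cohorts for analysis could also be read as allowing subjects to be grouped after results are seen.

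At stake is how a cohort difference is read. The cohort with the best result might be reported as the proven best algorithm when it is only a candidate.

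**Working it through.** **1. What depends on the phrase.** The sentence states an intention within the description of the treatment visit. The objective in the synopsis is feasibility and proof of concept. Neither the primary outcome (Section 3.1.1) nor the secondary outcomes (Section 3.1.2: WOMAC at Day 7 and duration of effect) contrasts cohorts. The protocol contains no between-cohort test, no rule for choosing a winner and no success criterion that uses one. The sample size is a cap with no calculation behind it, so there is no stated figure to reproduce.

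**2. How far chance could mislead.** This is an illustration only. From the protocol: N = 50 at most and five parameters that may vary. Assumed: K equal cohorts of n = 50/K, SD of VAS change between 2 and 3 on a 0-10 scale, one algorithm better than the rest by d points, choice by largest mean Day 7 improvement, no dropout.

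For K = 2, n = 25 and the probability that the better algorithm ranks first is Φ(d / (SD × √(2/25))). With d = 1:

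- SD 2.0: Φ(1/0.566) = 0.96
- SD 2.5: Φ(1/0.707) = 0.92
- SD 3.0: Φ(1/0.849) = 0.88

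For more cohorts, simulation (400,000 runs per setting) gives the values below; each range runs from SD 3 to SD 2.

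| Cohorts | 1 point better | 2 points better |
|---|---|---|
| 2 | 0.88-0.96 | 0.99-1.00 |
| 3 | 0.73-0.87 | 0.95-1.00 |
| 4 | 0.61-0.77 | 0.89-0.98 |
| 6 | 0.44-0.60 | 0.74-0.92 |

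Six cohorts (50/6 ≈ 8 subjects each) would arise from changing each of the five parameters once from a reference setting, 1 + 5 = 6. The protocol does not say this is done.

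Ranking and proof are different tasks. With two cohorts, SD 2.5 and d = 1, the better algorithm ranks first with probability 0.92, yet a two-sided 5% test has power of only Φ(1/0.707 − 1.96) ≈ 0.29. Choosing a candidate can work where proving superiority would not.

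**3. How far bias could mislead.** Suppose a systematic shift s favours the other cohort. With K = 2 and d = 1, the probability becomes Φ((1 − s) / (SD × √(2/25))). For s = 0.5 it is 0.72-0.81. If the same shift favours the better algorithm, 1 − s becomes 1.5 and the probability is 0.96-1.00. With two equally effective algorithms, a 0.5-point shift makes the favoured one rank first with probability 0.72-0.81 instead of 0.50. The protocol gives neither the size nor the direction of any such shift.

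**4. Whether the routes to bias are documented.** The exclusion in Section 2.5 applies to every cohort. It distorts a comparison only if the investigator knows the coming algorithm and applies the criterion differently. No section says that cohorts run one after another. All subjects receive active treatment, so expectation plainly threatens the before-after change; that it differs between algorithms is conjecture.

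**5. The cohort wording.** It is the algorithms that are placed into cohorts, and they are fixed beforehand by the sponsor. The natural reading is that a cohort is the set of subjects treated with a given algorithm. Further grouping rules are the kind of detail commonly left to an analysis plan.

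**The case for a change.** The best argument for a change is that it costs little and is right in substance. No analysis can supply randomisation afterwards, so the aim as worded cannot be met at any sample size. A stated purpose shapes how results are later described, and Section 3.3 marks the statistical analysis plan as not applicable, so nothing in the protocol tempers the claim at the analysis stage. Replacing the verb with language about identifying a candidate for confirmation would bring Section 2.6.2.2 into line with the synopsis without touching visits, sample size or data.

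What stands is that the verb is too strong, and that confounding is possible at any number of cohorts. The rest does not carry the argument. The choice by Day 7 VAS is an inference: the most effective method could equally be judged on duration, WOMAC or anticipated observations. The cohort number, SD, true difference and bias are all assumed, and Appendix C describes a scale of six faces, coarser than the continuous score used in the illustration. A ban on later regrouping would also be debatable in an exploratory study, because very small cohorts could then not be pooled.

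**Conclusion.** The phrase overstates what the design can deliver, but no change is needed. It is a loose statement of purpose, and the synopsis objective, the declared non-randomised and unblinded design, and the within-subject primary outcome already tell a reader how to take it. An analyst would describe cohort results side by side and treat the best-looking algorithm as a candidate, with or without an amendment. Rewording would need IRB approval under Section 5.3.2 and would leave every datum, analysis and result as it is.

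The ranking probabilities, from 0.88-0.96 with two cohorts to 0.44-0.60 with six for a 1-point advantage, hold only under the assumed equal cohorts, SD of 2 to 3, absence of bias and choice by Day 7 mean. They show why a cohort ranking should be read with caution. They do not show an error in the plan.

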### 2.6.2.3. Post-Treatment

Upon completion of treatment, the treatment area will be cleansed and the skin will be left undressed. Pressure to the treatment area with gauze 5-10 minutes may be applied to minimize bleeding. The subject will be instructed in post-treatment care.

The subject will be instructed to report any adverse events or treatment side effects (e.g., excessive redness, swelling, bruising, soreness, altered sensation, etc.) to the investigator between and at follow-up visits. Non-invasive ultrasound may be used to assess the volume and location of the

soft tissue treated below the dermis. Photography and videography of the treatment area may be obtained.

The subject will be scheduled and instructed for their follow-up visits and discharged from the clinic.

### 2.6.3. Visit 3/ Maintenance (Day 7) & Visit 4/Maintenance (Day 30)

Subject will be evaluated and data collected per the schedule of events. Any changes in concomitant medications/concurrent procedures will be assessed. Any anticipated observations, adverse events, and/or SAE/UADE of the previous treatment site(s) will be assessed and documented. Non-invasive ultrasound imaging of the treatment area may be captured. Photography may be taken of the treatment area.

